4.5.8.1 Fixed missing imputation based on Placebo distribution

To evaluate the robustness of the analysis of the second endpoint to the missing at random (MAR) assumption missing data of both treatment groups will be imputed by descriptive statistics derived from the distribution of the placebo group. For each visit the following descriptive statistics of FVC (mL) will be calculated from the placebo group only: lower quartile, median, upper quartile.

Pirfenidone — F. Hoffmann-La Roche Ltd

For each of the 2 treatment groups 3 datasets with imputed missing values will be created:

- Missing values imputed by median of placebo group for the respective visit
- Missing values imputed by lower quartile of placebo group for the respective visit
- Missing values imputed by upper quartile of placebo group for the respective visit

Then, within each of the 9 possible combinations of datasets two analyses will be performed:

The mean FVC decline in the treatment arms will be compared using a student's t-test. The mean FVC decline for each treatment arm will be calculated using the estimated FVC decline for each individual patient, which will be obtained by applying a linear regression model to the data over time of the respective patient.

The decline in FVC (mL) at week 24 will be estimated from a random slope and intercept model. This model will include fixed effects for treatment, the stratifying variables concomitant use of MMF and presence/absence of IPAF and treatment-by time-interaction. Random effects will be included for both time and intercept.

The difference between treatment groups will be calculated together with the corresponding p-value.

A table will present the results from the two analyses: estimates for the placebo group, pirfenidone group and the comparison pirfenidone versus placebo together with the respective p-value for each of the 9 combinations of imputed values.

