A summary table displaying the mean FVC decline together with two-sided 95% confidence intervals based on percentiles of the t-distribution will be provided by treatment arm. The mean FVC decline in each treatment arm will be compared using a student's t-test with a two-sided significance level α =0.05. Additionally, a two sample Wilcoxon test will be used for treatment comparison. Results of this test are of descriptive nature only.

The same analyses will be done by restricting the FVC decline values:

- Including patients with at least 3 site spirometry measurements Pirfenidone — F. Hoffmann-La Roche Ltd

- excluding patients with a predicted FVC decline below -1000 mL
- or above 1000 mL
- excluding values with a difference +/-50% from corresponding baseline site spirometry

Mean FVC declines and results from Student's t-test by subgroups (for definition see 4.5.6) will be displayed in a forest plot.

As a sensitivity analysis to the primary analysis, the time-adjusted mean FVC decline will be estimated by a repeated measures mixed model with patient effects fitted as random and day of measurement and treatment fitted as fixed effects. Please refer to Section 4.5.6 for further details.

A detailed description of SAS code to be used for the repeated measures mixed model is provided together with the respective table shell.

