4.5.8.2 Fixed missing imputation between Q1 and Q3 of Placebo distribution

In another approach to evaluate the robustness of the analysis of the second endpoint to the missing at random (MAR) assumption a tipping point sensitivity analysis will be performed, where missing data of both treatment groups will be imputed by values derived from the range between lower and upper quartile (Q1 - Q3) in the Placebo group at each visit. The aim of the tipping point approach is to assess how severe departures from MAR could be in order to reverse conclusions from the analysis of secondary endpoint under different assumptions for the decline after withdrawal of the randomized treatment.

100 datasets with imputed values will be created for each treatment group. For the first dataset missing values in the respective treatment group will be imputed by the lower quartile (Q1) of placebo group within each visit. In the second dataset, the missing values will be imputed by Q1 plus the amount of $0.01 \times (Q3 - Q1)$. The value added to Q1 will be increased within each subsequent dataset by another amount of $0.01 \times (Q3 - Q1)$, so that in the last of the 100 dataset the amount of Q3 from the placebo group will be imputed for missing values.

Pirfenidone — F. Hoffmann-La Roche Ltd

Then, for each of the 10000 combinations of datasets the decline in FVC (mL) at week 24 will be estimated from a random slope model This model will include fixed effects for the stratifying variables concomitant use of MMF and presence/absence of IPAF and treatment-by time-interaction. Random effects will be included for both time and intercept.

The difference between treatment groups will be calculated together with the respective p-value.

A heat map displaying positive and negative outcome based on the p-values for the comparison pirfenidone versus placebo with green and red colors (green: < 0.05, red: > 0.05) will be provided to illustrate the outcome of this analysis graphically. The robustness of the results will be discussed based on the magnitude of deviations from MAR required to change the results.

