4.5.8.3 Tipping point analysis with shifts

An additional approach is to evaluate the robustness of the analysis of the secondary endpoint to the missing at random (MAR) assumption by performing a tipping point sensitivity analysis using the Multiple Delta Adjustment Method.

As a first step non-monotone missing data will be imputed 100 times using MCMC (Markov Chain Monte Carlo) to generate 100 data sets of longitudinal spirometry data (FVC [mL]) with monotone missingness pattern (PROC MI). Such a missingness pattern is the pre-requisite for subsequently applying sequential imputation and means that once a patient has a missing FVC value at a particular time point, FVC values at all subsequent time points also have missing values. The seed in PROC MI number will be set to 1234.

Once the monotone missing pattern has been created, the tipping point analysis for the longitudinal FVC data will be based on the Multiple Delta Adjustment Method. Data in each of the 100 generated datasets with the monotone missingness pattern will be imputed once by using sequential regression. A delta adjustment will be added to each imputed value. The value of each delta adjustment will be given by shift parameters S_1 and S_2 for the 2 treatments.

For patients with more than one monotone missing visit, multiple adjustments must be applied and since the imputation method is sequential, the effect of the adjustments is cumulative. S1 and S2 therefore represent the slope of a linear adjustment over time. This step will be repeated for a variety of combinations of S1 and S2.

For each combination of shift values S1 and S2 the 100 complete data sets will be analyzed using the statistical model as described above. The estimate of treatment difference at week 24 will be derived. Rubin's rules (16) will be used to combine the results from the analyses for each pair of S1 and S2 (PROC MIIANALYZE). Point estimates for the comparison pirfenidone versus placebo and respective p-values will be reported for selected combinations of S1 and S2 in a cross-table.

The following combinations of S1 and S2 will be applied:

Pirfenidone — F. Hoffmann-La Roche Ltd

- S1 (Pirfenidone): -130, -125,-120,-115,-110,-105,-100,-95,-90,-85,-80,-75,-70,-65,-60,-55,-50,-45,-40,-35,-30,-25,-20,-15,-10,-5,0, 5, 10
- S2 (Placebo): -40,-35,-30,-25,-20,-15,-10,-5,0, 5, 10, 15, 20, 25, 30, 35, 40, 45, 50, 55, 60, 65, 70, 75, 80, 85, 90, 95, 100, 105, 110, 115, 120.

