A heat map displaying positive and negative outcome based on the p-values for the comparison pirfenidone versus placebo with green and red colors (green: < 0.05, red: > 0.05) will be provided to illustrate the outcome of this analysis graphically. The robustness of the results will be discussed based on the magnitude of deviations from MAR required to change the results (Rubin, 1987). Pharmacokinetic and Pharmacodynamic Analyses

No pharmacokinetic or pharmacodynamic analyses are planned for this study.

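### Two of the three missing-data checks on site FVC impute placebo quartiles of FVC level rather than change, and two heat maps colour a significant result green whichever arm it favours

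*SAP*

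**What the plan says.** SAP 4.5.8 plans three checks of the site-measured FVC decline against the missing-at-random assumption. It also says that no data were collected once treatment stopped.

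- **4.5.8.1** defines the fill values: "For each visit the following descriptive statistics of FVC (mL) will be calculated from the placebo group only: lower quartile, median, upper quartile". The chosen value goes into each missing visit in either arm. Each patient's line is then refitted and the arms compared by t-test, and a random slope and intercept model is also fitted.
- **4.5.8.2** starts the same way: "missing values in the respective treatment group will be imputed by the lower quartile (Q1) of placebo group within each visit". It then moves up in steps of 0.01 of the interquartile range, "so that in the last of the 100 dataset the amount of Q3 from the placebo group will be imputed for missing values". Its stated aim is to find departures that would "reverse conclusions from the analysis of secondary endpoint under different assumptions for the decline after withdrawal of the randomized treatment". The only output it names is this: "A heat map displaying positive and negative outcome based on the p-values for the comparison pirfenidone versus placebo with green and red colors".
- **4.5.8.3** imputes by sequential regression on the longitudinal data and adds cumulative shifts: "S1 and S2 therefore represent the slope of a linear adjustment over time". Its heat map is coloured "based on the p-values for the comparison pirfenidone versus placebo with green and red colors (green: < 0.05, red: > 0.05").

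Neither colour rule refers to the sign of the difference. The site FVC comparison follows the primary method (SAP 4.5.3), which is a "t-test with a two-sided significance level" of 0.05 (SAP 4.5.1).

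**The concern.** **Scale.** A patient who leaves at week 8 with a large lung volume and is then assigned the placebo median appears to collapse. A patient with a small lung volume appears to improve. Neither says anything about decline after stopping treatment, which is what 4.5.8.2 sets out to vary. Completers' slopes are untouched, and 4.5.8.3 does not have this fault because it uses the patient's own earlier values.

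**Colour.** Green stands for a positive outcome but means only p < 0.05. In the corners where pirfenidone dropouts get poor values and placebo dropouts good ones, the test can be significant against pirfenidone and still be shown as a success.

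**Stake.** A site FVC result that is robust to dropout could look fragile, and parts of the maps could be misread. SAP 3.2 and 4.5.2 describe serious quality problems with home spirometry, which makes the site result more important to readers.

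**Working it through.** **Inputs from the documents.** Declines of 85 and 60 mL, SD 70 mL, 125 per arm, two-sided 5%, 80% power (SAP 2.3). Site visits on days 1, 28, 56, 84, 112, 140 and 168 (Schedule of Assessments).

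**The plan's own figure.** SE = 70 × √(2/125) = 8.85 mL and 25/8.85 = 2.82, which gives 80.3% power on 248 degrees of freedom. The planned 125 per arm is reproduced.

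**Assumptions, not in the documents.** Baseline FVC mean 2300 mL, SD 700 mL (range 500–900). Random monotone dropout of 5, 10 or 20% in each arm, after 2 to 6 of the 7 visits. Residual SD 40 mL and true slope SD 53 mL per 24 weeks.

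**Step 1: effect on one patient.** Fitted change = 167 × Σ(d − d̄)y / Σ(d − d̄)², with d̄ = 84.14 and Σ(d − d̄)² = 21,785. The assumed SDs give √(53² + (167 × 40)²/21,785) ≈ 70 mL, as planned.

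Take two patients, each truly declining 85 mL, seen on days 1, 28 and 56 and then assigned 2250 mL:
- starting at 3000 mL: slope −5.693 mL/day × 167 = **−951 mL**
- starting at 1600 mL: slope +5.067 mL/day × 167 = **+846 mL**

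In general the fitted decline moves by k × (own level − imputed level), with k = 0.64, 1.07, 1.29, 1.29, 1.07, 0.64 for a patient last seen at week 0, 4, 8, 12, 16, 20. A between-patient SD of only 70/1.29 = 54 to 70/0.64 = 109 mL already adds as much spread as the planned 70 mL.

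**Step 2: effect on the comparison.** Approximate check at 10% dropout: the mean of k² over last-seen weeks 4 to 20 is 1.21. The variance is then about 0.9 × 70² + 0.1 × 1.21 × 700² = 4,410 + 59,290 = 63,700, an SD of about 252 mL. Simulation (1500 trials per setting, per-patient slopes, t-test, median fill in both arms), at 5/10/20% dropout:

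| Fill | Baseline SD (mL) | SD of fitted decline (mL) | Pirfenidone significantly better (%) |
|---|---|---|---|
| Level | 500 | 138/184/253 | 28/17/8 |
| Level | 700 | 180/249/349 | 20/11/6 |
| Level | 900 | 224/315/445 | 15/8/5 |
| Own baseline + placebo change | 700 | 64–68 | 76/74/67 |
| Complete data | – | 70 | 79 |

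Residual SD 60 with slope SD 17 mL moved the level-fill results by at most 1 point and the change-fill results by at most 2.

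**Step 3: the mixed model.** In 60 trials at 10% dropout, the random intercept and slope model gave t-values within 0.0002 of the slope t-test. Approximating the 4.5.8.2 model, which lists no treatment main effect, gave 21/12/8% significant with the level fill and 79/76/70% with the change fill.

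**Step 4: colour.** With pirfenidone at placebo Q1 and placebo at Q3, the cell significantly favours placebo, and is green, in 10/56/96% of trials at 5/10/20% dropout (baseline SD 500: 4/42/94%; SD 900: 15/64/97%). Over the whole 100 × 100 grid, wrong-direction green covers 0.5/4/12% of cells (400 trials).

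For 4.5.8.3, a cumulative shift of 1 mL per missed visit changes the fitted 24-week change by 0.64, 1.71, 3.00, 4.28 or 5.35 mL for 1 to 5 missed visits, mean 3.0. This assumes a regression coefficient near 1 on the previous visit. At S1 = −130 and S2 = +120 the expected difference is 25 − 250 × dropout × 3.0 = −12/−50/−125 mL, against pirfenidone. If patients last seen at baseline are also included, simulation gives about −16/−60/−148 mL, with the cell green for placebo in 10/85/100% of trials.

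**Step 5: end of the grid.** The first of 100 datasets is at Q1, so the last is at Q1 + 99 × 0.01 × (Q3 − Q1) = Q1 + 0.99(Q3 − Q1), not Q3.

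**The case against.** The strongest points on the other side:

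- **The scale in 4.5.8.2 is inferred.** It does not repeat that the quartiles are of FVC in mL, and 4.5.6 calls its model outcome a change while defining it as the measured value. However, 4.5.8.1 is explicit, 4.5.8.2 continues from it, and 4.5.6 concerns the model outcome, not the imputed statistic. If change was meant in 4.5.8.2, it has to be written.
- **The fault is not only variance.** This is right. When the arms get different quartiles the mean shifts too. That shift is also on the level scale, so it is part of the same fault.
- **The colour rule has limited reach.** This stands. It does not move the first tipping point, and a reader crosses red before reaching wrong-direction green. Estimates are tabulated in 4.5.8.1 and for selected cells of 4.5.8.3. In 4.5.8.2 the difference is calculated, but no table is promised. At 5% dropout the extreme shift cell, −12 mL against an SE of at least 8.9 mL, would usually be red.
- **The change-based fill is also a fixed single value.** True: it understates uncertainty and ignores the last observed value. It is no more deterministic than the planned fill, and the overall SD stays at 64–68 mL against 70.
- **Low stakes and a sound alternative.** The trial is hypothesis-generating, the p-values are descriptive, and the imputation in 4.5.8.3 is sound. The median level fill tends to hide a real effect, not to create one. This limits the severity but does not make the two checks informative.

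**Conclusion.** The concern holds. As written, 4.5.8.1 and 4.5.8.2 do not test assumptions about decline after dropout. Where both arms get the same quartile they mainly add variance; elsewhere they add a mean shift driven by lung volume. With a baseline SD of 500–900 mL and 5–20% dropout, the chance that the planned effect stays significant under the median fill falls to 5–28%, against 67–76% with a change-based fill (baseline SD 700 mL). The direction of this result does not depend on the exact spread, because about 54–109 mL between patients is already enough to matter. The actual size depends on the trial's dropout and FVC spread, which the documents do not give.

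The colour rule is a smaller, separate error: negligible across the 4.5.8.2 grid at 5% dropout and material at 20%. The grid endpoint is a minor slip. Overall this should be fixed. It affects how robustness of a secondary endpoint is reported, not the primary analysis.

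**What to change.** 1. In 4.5.8.1 and 4.5.8.2, compute the placebo lower quartile, median and upper quartile of change from baseline in FVC (mL) at each visit, and impute the patient's own baseline plus that change. State the scale explicitly in both sections.
2. In the 4.5.8.2 and 4.5.8.3 heat maps, use green only when p < 0.05 and the estimate favours pirfenidone, red when p ≥ 0.05, and a third colour when p < 0.05 favours placebo.
3. In 4.5.8.2, use a step of (Q3 − Q1)/99, which keeps 100 datasets per arm and 10,000 combinations, or use 101 datasets.

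The cost is SAP wording and small program changes, with no new data. Because the primary analysis was done in March 2019, the change must be disclosed as post hoc, and any results already produced under the current rule should be shown beside the revised ones.

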4.5.8.2 Fixed missing imputation between Q1 and Q3 of Placebo distribution

In another approach to evaluate the robustness of the analysis of the second endpoint to the missing at random (MAR) assumption a tipping point sensitivity analysis will be performed, where missing data of both treatment groups will be imputed by values derived from the range between lower and upper quartile (Q1 - Q3) in the Placebo group at each visit. The aim of the tipping point approach is to assess how severe departures from MAR could be in order to reverse conclusions from the analysis of secondary endpoint under different assumptions for the decline after withdrawal of the randomized treatment.

100 datasets with imputed values will be created for each treatment group. For the first dataset missing values in the respective treatment group will be imputed by the lower quartile (Q1) of placebo group within each visit. In the second dataset, the missing values will be imputed by Q1 plus the amount of $0.01 \times (Q3 - Q1)$. The value added to Q1 will be increased within each subsequent dataset by another amount of $0.01 \times (Q3 - Q1)$, so that in the last of the 100 dataset the amount of Q3 from the placebo group will be imputed for missing values.

Pirfenidone — F. Hoffmann-La Roche Ltd

Then, for each of the 10000 combinations of datasets the decline in FVC (mL) at week 24 will be estimated from a random slope model This model will include fixed effects for the stratifying variables concomitant use of MMF and presence/absence of IPAF and treatment-by time-interaction. Random effects will be included for both time and intercept.

The difference between treatment groups will be calculated together with the respective p-value.

A heat map displaying positive and negative outcome based on the p-values for the comparison pirfenidone versus placebo with green and red colors (green: < 0.05, red: > 0.05) will be provided to illustrate the outcome of this analysis graphically. The robustness of the results will be discussed based on the magnitude of deviations from MAR required to change the results.

4.5.8.3 Tipping point analysis with shifts

An additional approach is to evaluate the robustness of the analysis of the secondary endpoint to the missing at random (MAR) assumption by performing a tipping point sensitivity analysis using the Multiple Delta Adjustment Method.

As a first step non-monotone missing data will be imputed 100 times using MCMC (Markov Chain Monte Carlo) to generate 100 data sets of longitudinal spirometry data (FVC [mL]) with monotone missingness pattern (PROC MI). Such a missingness pattern is the pre-requisite for subsequently applying sequential imputation and means that once a patient has a missing FVC value at a particular time point, FVC values at all subsequent time points also have missing values. The seed in PROC MI number will be set to 1234.

Once the monotone missing pattern has been created, the tipping point analysis for the longitudinal FVC data will be based on the Multiple Delta Adjustment Method. Data in each of the 100 generated datasets with the monotone missingness pattern will be imputed once by using sequential regression. A delta adjustment will be added to each imputed value. The value of each delta adjustment will be given by shift parameters S_1 and S_2 for the 2 treatments.

For patients with more than one monotone missing visit, multiple adjustments must be applied and since the imputation method is sequential, the effect of the adjustments is cumulative. S1 and S2 therefore represent the slope of a linear adjustment over time. This step will be repeated for a variety of combinations of S1 and S2.

For each combination of shift values S1 and S2 the 100 complete data sets will be analyzed using the statistical model as described above. The estimate of treatment difference at week 24 will be derived. Rubin's rules (16) will be used to combine the results from the analyses for each pair of S1 and S2 (PROC MIIANALYZE). Point estimates for the comparison pirfenidone versus placebo and respective p-values will be reported for selected combinations of S1 and S2 in a cross-table.

The following combinations of S1 and S2 will be applied:

Pirfenidone — F. Hoffmann-La Roche Ltd

- S1 (Pirfenidone): -130, -125,-120,-115,-110,-105,-100,-95,-90,-85,-80,-75,-70,-65,-60,-55,-50,-45,-40,-35,-30,-25,-20,-15,-10,-5,0, 5, 10
- S2 (Placebo): -40,-35,-30,-25,-20,-15,-10,-5,0, 5, 10, 15, 20, 25, 30, 35, 40, 45, 50, 55, 60, 65, 70, 75, 80, 85, 90, 95, 100, 105, 110, 115, 120.

A heat map displaying positive and negative outcome based on the p-values for the comparison pirfenidone versus placebo with green and red colors (green: < 0.05, red: > 0.05) will be provided to illustrate the outcome of this analysis graphically. The robustness of the results will be discussed based on the magnitude of deviations from MAR required to change the results (Rubin, 1987). Pharmacokinetic and Pharmacodynamic Analyses

No pharmacokinetic or pharmacodynamic analyses are planned for this study.

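### In the delta-adjusted tipping-point analysis, S1 and S2 are not in general the slope of a linear adjustment, so the departure from MAR at the tipping point cannot be read from S

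*SAP*

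**What the plan says.** SAP version 3.0, Section 4.5.8.3, is the third of three missing-data sensitivity approaches for the secondary endpoint. Intermittent gaps are first filled by MCMC. Each of the 100 datasets "with the monotone missingness pattern will be imputed once by using sequential regression". Then "A delta adjustment will be added to each imputed value", and "The value of each delta adjustment will be given by shift parameters S_1 and S_2 for the 2 treatments".

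For patients with several missed visits the SAP argues that "since the imputation method is sequential, the effect of the adjustments is cumulative", and from this it concludes that "S1 and S2 therefore represent the slope of a linear adjustment over time". The grid runs from -130 to +10 for pirfenidone and from -40 to +120 for placebo, in steps of 5. The reading rule is: "The robustness of the results will be discussed based on the magnitude of deviations from MAR required to change the results".

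The section does not name the predictors in the sequential regression, gives no unit for S, and does not plan to report the shift actually reached at Week 24.

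**The concern.** A cumulative adjustment need not be a linear one. In a sequential imputation, the shift given at one visit reaches the next only through the regression coefficients on visits already imputed. Weight that falls on observed visits carries no shift. The accumulated shift can therefore flatten, or in some structures steepen, relative to a straight line.

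This matters because S is the scale on which robustness will be judged. A reader told that S is a slope will multiply it by the number of missed visits to see how severe a departure was tested. SAP Section 4.5.8 says nothing was collected after treatment discontinuation, so early drop-outs miss several visits in a row. That is where S and the realised shift can part company.

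**Working it through.** **Inputs from the documents.** Site FVC at baseline and every 4 weeks to Week 24, so seven visits. The same S is added at each imputed visit. SAP Section 4.5.6 models site FVC with random intercept, random slope and independent errors, and I use that as the covariance structure.

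**Assumptions, because the documents give no values.** Between-patient SD 700 mL; slope SD 0–150 mL per 24 weeks; visit SD 30–150 mL; S in mL; and two alternative predictor sets, all earlier visits or the preceding visit only. The regression coefficients are taken not to depend on S.

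**The plan's property.** If S is a slope per visit, the shift at the k-th missed visit is k × S.

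**What the procedure gives.** Let s(j) be the mean shift at visit j in units of S, with s = 0 at observed visits. Then

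s(j) = 1 + Σ b(j,i) × s(i), summed over the predictors i,

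with b(j) = V(pp)⁻¹ V(pj), where V has elements 700² + τ² t(i)t(j), plus σ² on the diagonal, and t runs from 0 to 1 in sixths.

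**One case in full.** Slope SD τ = 70, visit SD σ = 100, all earlier visits as predictors, Weeks 16, 20 and 24 missing:
- Week 16: all predictors are observed, so s = 1.
- Week 20: the weight on Week 16 is 0.271, so s = 1 + 0.271 = 1.271.
- Week 24: the weights on Weeks 16 and 20 are 0.224 and 0.263, so s = 1 + 0.224 × 1 + 0.263 × 1.271 = 1.56.

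The linear reading is 3.

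**Week 24 shift in units of S**

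| Missed visits k | Linear reading | All earlier visits, SDs 700/70/100 | All earlier visits, slope SD 0–150, visit SD 30–150 | Preceding visit only, SDs 700/70/100 |
|---|---|---|---|---|
| 1 | 1 | 1.00 | 1.0 | 1.00 |
| 2 | 2 | 1.26 | 1.2–1.6 | 1.98 |
| 3 | 3 | 1.56 | 1.4–2.5 | 2.94 |
| 4 | 4 | 1.89 | 1.6–3.8 | 3.89 |
| 5 | 5 | 2.29 | 1.9–5.6 | 4.82 |
| 6 | 6 | 2.82 | 2.4–7.5 | 5.72 |

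The lower ends come from slope SD 0. The upper ends come from slope SD 150 with visit SD 30, where five and six missed visits give 5.61 and 7.53, above k in the second case by a quarter. An error-free random walk gives exactly k.

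**In mL.** S1 = -100 with the last three visits missing reads as -300 mL at Week 24. With all earlier visits as predictors the applied shift is about -140 to -250 mL (1.4 and 2.5 × 100), and -156 mL in the case worked above. With the preceding visit only it is -294 mL.

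**Cross-check against the planning SD.** The only variability figure in the documents is the 70 mL SD of decline in SAP Section 2.3, a planning value for home FVC. A fitted 24-week decline over seven visits has variance τ² + 1.286 σ². The case worked above implies √(70² + 1.286 × 100²) = 133 mL, so it is noisier than that figure. Tying the two together by τ² + 1.286 σ² = 70², with all earlier visits as predictors, the Week 24 shift for three missed visits is 0.46, 0.59 and 0.69 of linear at τ = 0, 50 and 60. At τ = 69 (σ about 10) it is 0.86 for three missed visits and 1.45 for six. The pattern is the same.

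**The case against.** The strongest reply is that the documents cannot show the linear reading to be wrong in this trial. The SAP says only that sequential regression is used. If the preceding visit is the sole predictor, the realised shift is 98% of linear after three missed visits (2.94/3) and 95% after six (5.72/6). This stands: partial carry-over is not a necessary property of the method.

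A reader might infer that the tested departure from MAR is definitely overstated. The documents do not support that either. The predictor set and covariance are not given, and when slope variance dominates, the realised shift for patients missing five or six visits can exceed k × S, so the departure would be understated.

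A reader might also infer that the tipping-point analysis is invalid. It is not. Each estimate and p-value is valid for the imputation actually run at that S1/S2 pair.

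It can further be said that the SAP tabulates point estimates for selected pairs, so comparison with the unshifted pair would show how far the treatment difference moved. That helps, but only if the unshifted pair is among those selected, and it gives the net difference rather than the shift in each arm. Finally, the tested shifts stay large even when flattened: 1.56 × -130 = -203 mL for three missed visits, against a planned placebo decline of 85 mL. The analyses in Sections 4.5.8.1 and 4.5.8.2 impute explicit values without a sequential shift. Both points limit the consequence; neither makes the sentence correct.

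**Conclusion.** The inference from a cumulative adjustment to a linear one is wrong as written. S is a conditional shift added at each imputed visit, and what it accumulates to depends on a regression that the SAP does not specify. With all earlier visits as predictors and ordinary measurement error, reading S as a slope probably overstates the Week 24 departure: by about 1.2 to 2.1 times for three missed visits (3/2.5 to 3/1.4) over the assumed SDs. For six missed visits the factor runs from about 0.8 to 2.5 (6/7.5 to 6/2.4), so the direction is not fixed. These figures rest on assumed SDs and an assumed predictor set; the tipping point itself cannot be computed without data.

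Only the interpretation of S is affected, and with it the stated size of the departure from MAR needed to change the result. The severity is modest: this is one of three sensitivity approaches for a secondary endpoint whose p-values are descriptive, in a trial described as hypothesis-generating.

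**What to change.** Choose one of two routes.

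1. Impute the monotone missing visits under MAR with no shift inside the sequence, then add k × S to the value at the k-th missed visit. S is then a slope per visit by construction, and the linear-slope sentence becomes true.
2. Keep the recursive shift, delete the linear-slope sentence, name the predictors in the sequential regression, describe S as a per-visit conditional shift, and print the mean realised Week 24 shift by arm beside each reported S1/S2 pair. Discuss robustness on that realised scale.

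The first route costs a rerun of an existing program; the second costs wording and one extra output. Under either, the tipping point may look less favourable than a slope reading of S suggests.
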